3.3 Definition of Baseline values

Section 8.3.4 details the derivation of the Baseline value for the HSSDD assessment. For all other assessments, the below applies.

A Baseline value for a participant is defined as the latest non-missing measurement for that participant up to and including the day of administration of first study medication, unless otherwise stated. If a Baseline assessment is taken on the same day as first administration of study medication, it is eligible to be used as the Baseline value, even in the case that the time of the assessment is recorded as taking place after the time of first study medication administration. This is considered acceptable as this measurement is still the best representation of the Baseline value of the given assessment since it is highly unlikely that the study medication could have an impact on any measurement in such a short period of time. However, such cases should be rare as study center personnel are instructed to do all assessments at the Baseline visit prior to administering study medication. One exception to this rule is plasma concentration of bimekizumab. If Baseline plasma concentration is measured at a time after the first administration of study medication, then it will not be eligible to be considered as a Baseline plasma concentration. Such cases will be discussed with the quantitative clinical pharmacologist.

For randomized participants for whom no start date of treatment is available, the Baseline value will be considered as the last available value on or before the randomization date.

If a Baseline measurement is missing or not collected, and a Screening value is available, the Screening value will be utilized as Baseline instead.

Baseline values for component scores should be computed using components from the same visit where the relevant measurements were recorded prior to dosing. For example, if the Screening visit has all of the components, but the Baseline visit is missing 1 or more components, the Baseline value for the component score should be calculated using the Screening visit values.

When the time of first dose is derived, it will be based on the first injection of study treatment, regardless of whether or not it is an active treatment.

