7 MEASUREMENTS OF TREATMENT COMPLIANCE

Due to the method of administration of the treatments, compliance will be examined in terms of completed injections.

Treatment compliance will be calculated as:

$$\frac{N_{actual}}{N_{expected}} \times 100\%$$

where N_{actual} is the total number of actual (completed) injections, and $N_{expected}$ is the total number of expected injections. In this study, dosing occurs [REDACTED] from Week 0 to Week 46, where 2 injections are administered at each given visit either with active dosing or placebo injection. It is expected that a participant should complete a total of 48 injections by the end of study. If a participant discontinues early, then the number of expected injections is based on the time of early discontinuation relative to the dosing visits. For example, if a participant discontinues after Week 8 visit and prior to Week 10 visit, the total number of expected injections will be 10.

A summary of percent treatment compliance categorized as <75% and ≥75% will be provided by treatment group for each study period (Initial Treatment Period for the RS, Maintenance Treatment Period for the MS, and the combined Initial and Maintenance Treatment Period for the AMS).

A by-participant listing of treatment compliance will be provided.

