9 PHARMACOKINETICS AND PHARMACODYNAMICS

9.1 Pharmacokinetics

Pharmacokinetic variables will be analyzed for all participants in the PK-PPS. Bimekizumab plasma concentrations will be summarized for each treatment at each scheduled visit.

PK summaries will be based on observed values. No imputation will be used. However, if plasma concentration measurements are below the level of quantification (BLQ), then for calculation of the derived statistics the result will be set to ½ of the lower level of quantification (LLOQ). Descriptive statistics including geometric mean, geometric coefficient of variation, and geometric mean 95% CI if applicable will be calculated if at least 2/3 of the values of interest are above the LLOQ. If this is not the case, only median, minimum, and maximum will be presented.

Geometric mean plasma concentration will be plotted by treatment group, and by cumulative antibody status for participants randomized to bimekizumab on linear and log linear scale. In addition, HiSCR₅₀ response (0=not achieved, 1=achieved) assessed at each PK visit (excluding Week 1) will be plotted against the visit's bimekizumab plasma concentration, separated by treatment group. Spaghetti plots of bimekizumab plasma concentrations by week from bimekizumab first dosing separated by treatment group and antibody status will be presented for participants with and without HiSCR₅₀ response at Week 16.

If the dosing for a visit is +/- 7 days out of window, then the plasma concentration from that visit and all subsequent visits will be excluded from the PK summary. In addition, if the PK sampling date is >1 day after the dosing date, then the plasma concentration from that visit will be excluded from the PK summary.

All PK concentrations collected will be listed irrespective of the dosing or sampling occurring out of window.

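### The PK out-of-window rule is not limited to bimekizumab doses, so read literally a late or early placebo injection removes all of a participant's later concentrations from the PK summary

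*SAP*

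**What the plan says.** SAP Section 9.1 (Pharmacokinetics) has two exclusion rules for the PK summary. The first concerns dosing time: "If the dosing for a visit is +/- 7 days out of window, then the plasma concentration from that visit and all subsequent visits" are excluded. The second concerns sampling time and acts on one visit only: "if the PK sampling date is >1 day after the dosing date, then the plasma concentration from that visit will be excluded". All concentrations are listed whatever the timing.

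Section 7 (Measurements of Treatment Compliance) describes what happens at a dosing visit between Week 0 and Week 46: "2 injections are administered at each given visit either with active dosing or placebo injection". Section 2.3.2.2 has one arm on placebo until Week 16 and on bimekizumab from Week 16 to Week 48; Section 2.4 plans 70 participants for it.

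Elsewhere the SAP names bimekizumab when it means bimekizumab. Section 3.2.1 counts relative day from the first IMP dose and, for the placebo-start arm, also from the first bimekizumab dose. Sections 10.1.1.1 and 10.1.2.1 use the last bimekizumab dose, rather than the last dose, where an arm has a different dosing interval.

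**The concern.** The dosing rule in Section 9.1 lacks the qualifier that the exposure sections carry. A programmer who follows the text would test every dosing date against the window, including dates on which only placebo was injected.

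A placebo injection given at the wrong time cannot change a bimekizumab concentration at a later visit. The rule would nevertheless discard that participant's concentrations from then on. In the placebo-start arm, one out-of-window visit before Week 16 would remove the whole Week 16 to 48 bimekizumab record. In an arm with a longer bimekizumab interval, an out-of-window placebo-only visit would remove everything after it. The by-visit geometric means and confidence intervals would lose valid data for a reason unrelated to exposure.

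**Working it through.** **1. The dosing schedule, from the plan's own figures.** The interval between dosing visits is redacted, but Section 7 says "It is expected that a participant should complete a total of 48 injections by the end of study" and, for a participant stopping after the Week 8 visit and "prior to Week 10 visit, the total number of expected injections will be 10". At 2 injections per visit:

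| Interval | Visits, Weeks 0–46 | Injections | Injections through Week 8 |
|---|---|---|---|
| 1 week | 47 | 94 | 18 |
| 2 weeks | 24 | 48 | 10 |
| 4 weeks | 12 | 24 | 6 |

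Only the 2-week interval reproduces both 48 and 10, so there are 24 dosing visits.

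**2. Placebo-only visits that can trigger the rule, placebo-start arm.** Dosing visits before Week 16 fall at Weeks 0, 2, 4, 6, 8, 10, 12 and 14: eight visits, all placebo. Section 3.1 counts visit windows from the date of first dose. Week 0 is therefore the anchor and cannot be out of window, which leaves seven visits (Weeks 2 to 14). Because windows run from the first dose, one badly timed visit does not move the scheduled dates of later ones; bimekizumab dosing from Week 16 can be on schedule.

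**3. Placebo-only visits, longer-interval arm.** The bimekizumab interval is redacted. If it were 4, 6 or 8 weeks (assumed), 12, 16 or 18 of the 24 visits would be placebo only. No percentage is attached here, because the count itself is an assumption.

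**4. Illustrative size, placebo-start arm.** The SAP gives no rate of visits this far out of window. Assume a rate p per visit, independent across visits, with every participant attending all seven. The proportion with at least one such visit is 1 − (1 − p)^7.

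- p = 0.005: 1 − 0.995^7 = 3.4%; × 70 = 2.4, about 2 participants
- p = 0.01: 1 − 0.99^7 = 6.8%; × 70 = 4.8, about 5 participants
- p = 0.03: 1 − 0.97^7 = 19.2%; × 70 = 13.4, about 13 participants

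**5. Does another rule prevent this?** Section 3.5.8 defines the PK-PPS by at least one full bimekizumab dose, a quantifiable post-dose concentration, and no important deviation that would affect the PK. A mistimed placebo injection would not affect the PK, so such a participant can belong to the PK-PPS and then contribute nothing to the summary from the trigger visit on. Nothing in Section 9.1 restores the data.

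**The case against.** The strongest reply is that the SAP never says placebo injections trigger the rule. 'Dosing' is undefined in Section 9.1, and in a PK section a reader may take it to mean the study drug. That is fair: this is the literal reading of an ambiguous term, not an explicit instruction. But the SAP makes the distinction in Sections 3.2.1, 10.1.1.1 and 10.1.2.1, and its absence here invites the literal reading.

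The consequence is also limited. PK is one of the other objectives in Section 2.1.3, the output is descriptive, and the listings are complete. The rates in the illustration are assumed; with a ±3-day visit window, nothing in the SAP suggests that as many as 3% of visits would be this far out. Section 9.1 speaks of the PK summary and does not say whether the concentration plots lose the same values.

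Two stronger readings are tempting, and the document does not support either:

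- *Concentrations after a missed bimekizumab dose wrongly stay in.* Neither rule in Section 9.1 mentions a dose not given. But all PK analysis is confined to the PK-PPS, which removes participants with important PK-affecting deviations, and Section 3.4 places the deviation criteria in a separate document. It cannot be shown from the SAP that such data remain.
- *Samples taken after the injection wrongly stay in.* The sampling rule removes only those more than a day late, while Section 3.3 says "If Baseline plasma concentration is measured at a time after the first administration of study medication, then it will not be eligible". That sentence concerns eligibility as Baseline. The SAP nowhere requires later samples to be pre-dose. It does not make Week 16 the PK Baseline of the placebo-start arm either; the Week 16 Baseline in Section 9.3.2 is for antibodies.

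**Conclusion.** The point holds as a drafting defect in a stated rule. As written, the carry-forward exclusion in Section 9.1 covers placebo injections and would permanently remove valid bimekizumab concentrations for a reason that cannot bear on exposure. The clearest case is the placebo-start arm, where seven placebo-only visits can trigger it before any bimekizumab is given. The size depends on an unknown rate: about 2 to 13 of 70 participants under assumed rates of 0.5% to 3% per visit, independence between visits and full attendance through Week 14. No hypothesis test or efficacy estimate is affected. It is worth correcting because the loss is avoidable and the correction is a phrase.

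**What to change.** Restrict the trigger in Section 9.1 to bimekizumab. Suggested sense: where a bimekizumab dose is given more than 7 days out of window, the concentration at that visit and those at every later visit leave the PK summary; where an out-of-window visit involved placebo injections only, at most that visit's own concentration is left out.

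Keep the existing rule on samples taken more than one day after dosing. It still prevents a late sample at a placebo-only visit from being summarised under the nominal visit.

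The cost is a wording change plus use of the treatment codes to tell bimekizumab from placebo dosing dates. No new data are needed, and the listings do not change.

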9.2 Pharmacodynamics

Not applicable.

9.3 Immunogenicity

9.3.1 Autoantibodies

Not applicable.

9.3.2 Anti-bimekizumab antibodies

Anti-bimekizumab antibodies (ADAb) will be measured using a 3-tiered assay approach: screening assay, confirmatory assay, and titration assay. Samples confirmed as positive within the confirmatory assay will be further evaluated for the presence of neutralizing anti-bimekizumab antibodies specific to IL-17AA, IL-17FF or both. Samples will be taken at Baseline, then at study Weeks 4, 8, 12, 16, 20, 24, 36 and 48, and at PEOT and SFU timepoints.

ADAb samples are not analyzed when study participants are on a treatment other than bimekizumab. For study participants who switch from placebo to bimekizumab, samples are analyzed starting at the visit when the switch to bimekizumab occurs (Week 16). The sample at Week 16 will act as the Baseline for that treatment group.

The screening cut point will be used to determine the status of anti-bimekizumab antibodies in the test sample as Positive Screen (PS) or Negative Screen (NS). For samples presenting anti-bimekizumab antibody levels that are PS, a further confirmatory assay will be performed, and the result of which will be reported as either Positive Immunodepletion (PI) or Negative Immunodepletion (NI).

ADAb status for each sample will be derived as follows:

- Sample values that are either NS, or PS and NI and where the bimekizumab concentration is less than the validated ADAb assay drug tolerance limit will be defined as anti-bimekizumab antibody negative.
- Sample values that are either NS, or PS and NI and where the bimekizumab concentration exceeds the validated ADAb assay drug tolerance limit will be defined as inconclusive.

- Sample values that are PS and PI will be defined as ADAb positive (regardless of availability of a titer value)
- Missing or non-evaluable samples will be defined as missing

Positive immunodepletion samples will be titrated, and the ADAb titer (reciprocal dilution factor including minimum required dilution) will be reported. Subsequently, PI samples will also be subject to a neutralizing assay to evaluate the potential of ADAb to neutralize the target binding of bimekizumab (IL-17AA or IL-17FF or both) in vitro.

Cumulative ADAb status will be derived as follows:

The ADAb status (positive, negative or missing) will be considered in a cumulative manner at each time point.

A study participant will be counted positive from the first visit at which the study participant achieved a positive ADAb sample result to the end of the treatment period, regardless of any missing/inconclusive or negative ADAb sample result.

If a study participant has only negative ADAb samples or only one missing/inconclusive sample with all other ADAb samples being negative, the study participant will be classified as negative. An exception remains for the Baseline Visit where only one sample could be available. If the sample is missing/inconclusive, then the sample will be classified as being negative for the cumulative ADAb status.

Otherwise, the study participant will be classified in the missing ADAb category.

Overall ADAb status will be derived as follows:

A study participant will be classified as:

- Positive if the study participant has at least one positive sample up to the time point of interest (regardless of having missing/inconclusive data).
- Negative if the study participant has all the samples negative or only one missing/inconclusive sample with negative ADAb samples up to the timepoint of interest.
- Missing if the study participant has more than one missing ADAb result (or have more than one inconclusive sample) and all other available ADAb samples are negative up to the time point of interest.

ADAb categories will be derived as follows:

- **Pre ADAb negative – treatment-emergent ADAb negative (Category 1):** Includes study participants who are anti-bimekizumab antibody negative at Baseline and anti-bimekizumab antibody negative at all sampling points during the period of interest (one post-Baseline missing/inconclusive sample is allowed for subjects with pre- anti-bimekizumab antibody negative sample). This group also includes study participants who have a missing or inconclusive sample (either missing or inconclusive or insufficient volume) at Baseline (ie, pre-treatment) with all post-Baseline samples as ADAb negative.
- **Pre ADAb negative – treatment-emergent ADAb positive (Category 2):** Includes study participants who are ADAb negative at Baseline and ADAb positive at any sampling points post-Baseline during the period of interest. This group also includes study participants who

have a missing sample (either missing or insufficient volume) at Baseline (ie, pre-treatment) with 1 or more post-Baseline samples as ADA_b positive.

- **Pre ADA_b positive – treatment-emergent reduced ADA_b (Category 3):** Includes study participants who are ADA_b positive at Baseline, and ADA_b negative at all sampling points post-Baseline during the period of interest.
- **Pre ADA_b positive – treatment-emergent unaffected ADA_b positive (Category 4):** Includes study participants who are ADA_b positive at Baseline and are ADA_b positive at any sampling point post-Baseline during the period of interest with titer values of the same magnitude as Baseline (ie, less than a predefined fold difference from the Baseline titer).
 - For this analysis, this is set at an increase of less than the validated Minimum Significant Ratio (MSR) of 2.07-fold from Baseline.
- **Pre ADA_b positive – treatment-emergent ADA_b boosted positive (Category 5):** Includes study participants who ADA_b positive at Baseline and are ADA_b positive at any sampling point post-Baseline during the period of interest with increased titer values compared to Baseline (equal to or greater than a predefined fold difference increase from Baseline titer which will be defined within the validation of the assay).
 - For this analysis, this is set at an increase equal to or greater than the validated MSR of 2.07-fold from Baseline.
 - Note: for any study participant who is ADA_b positive at Baseline and ADA_b positive at a post-Baseline time point during the period of interest, but for whom titers are not available to determine treatment unaffected or treatment boosted status, the study participant will be considered as treatment boosted, assuming no other samples are available.
- **ADA_b Inconclusive (Category 6):** Includes study participants who have an ADA_b positive Baseline (pre-treatment) sample and some post-Baseline samples during the period of interest are missing or inconclusive, while other post-Baseline samples are ADA_b negative.
- **Total treatment-emergent ADA_b positivity (Category 7 [Categories 2 and 5 combined]):** Includes study participants who are pre ADA_b negative – treatment-emergent ADA_b positive (Category 2) and pre ADA_b positive – treatment boosted ADA_b positive (Category 5).
- **Total prevalence of pre- ADA_b positivity (Category 8 [Categories 3, 4, 5 and 6 combined]):** Study participants that are tested ADA_b positive at Baseline.
- **Missing:** Includes study participants who are ADA_b negative, missing, or inconclusive at Baseline with some post-Baseline samples as missing or inconclusive, and other samples as ADA_b negative.

For purposes of efficacy subgroup analyses based on anti-bimekizumab antibody status, the following categories can also be used:

- ADA_b positive – This is defined as study participants who are anti-bimekizumab antibody positive on at least 2 time points while on treatment (ie, excluding Baseline, excluding SFU).
- ADA_b negative – Study participants for who either:

- All samples (including Baseline) are ADAb negative and there are no missing or inconclusive samples
- Only 1 sample is ADAb positive and all other samples (including Baseline) are ADAb negative or missing or inconclusive
- Only 1 sample is missing or inconclusive and the remaining ADAb samples are negative.
- ADAb missing - Defined as study participants who do not fulfil the criteria for one of the 2 groups listed above.

The rationale for requiring at least 2 time points in which ADAb levels are above the specified cut point is to exclude those study participants who have only one occurrence of ADAb levels during the course of treatment. Including such study participants would increase the number of ADAb positive study participants with potentially no impact on efficacy.

In the case that a sample is collected 1 or more days following the scheduled visit date in which the drug was administered, the ADAb results for that sample will be associated with the scheduled visit and summarized accordingly. Such samples will also be considered when ADAb results are summarized over a given study period.

Analysis

Immunogenicity will be assessed through summary tables and figures, and listing of individual results by participants. All analyses will be run on the AMS, unless specified otherwise.

- Summary of ADAb status overall and by each visit separated by treatment group
- Summary of the time-point of the first occurrence of ADAb positivity during the treatment period by treatment group. A plot of the titer by time to first ADAb positivity will be prepared.
- All individual participant-level ADAb results will be listed.
- The number and percentage of participants in each of the 8 ADAb categories during the treatment period by treatment group.
- The prevalence of immunogenicity, separated by treatment group, and defined subcategory, will be reported by visit, defined as (cumulative) proportion of participants having confirmed positive ADAb samples at any visit up to and including that visit. Missing samples will not be included in the denominator.
- The time to achieving treatment-emergent ADAb positivity, separated by treatment group and defined subcategory, will be analyzed based on Kaplan-Meier methods. This will be shown only for Categories 2 and 8 above. Participants will be considered to have an event at the time point at which treatment emergent ADAb positive is first achieved (taking the MSR into consideration for sub-category 5). Participants classified as treatment-emergent ADAb negative will be censored at the time of the last available ADAb result.
- A summary of HiSCR₅₀ responders at Week 16, separated by treatment group, as a function of ADAb titer will be presented graphically.
- Individual plots of plasma bimekizumab concentrations/ ADAb titer both plotted on the Y-axes by visit (x-axis) for the full treatment period (excluding SFU for interim analyses and

including SFU for final analyses) will be presented for participants with and without HiSCR₅₀ response at Week 16.

- Spaghetti plots of ADA_b titer (y-axis) by visit (x-axis), separated by treatment group for all ADA_b positive participants, including Baseline positive participants.
- Box plots of ADA_b titer (logscale) by time to first ADA_b positivity by treatment group.

The groups for defining ADA_b status for safety subgroup analyses are as follows:

- AEs starting before first ADA_b positive result
- AEs starting on or after first ADA_b positive result
- AEs for participants who were always ADA_b negative

This is further explained in Section 10.2.2

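### The efficacy ADAb grouping labels one confirmed positive with any number of missing or inconclusive samples ADAb negative, which can attenuate an ADAb-related loss of response

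*SAP*

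**What the plan says.** Section 4.8 lists antibody positivity as a subgroup for HiSCR50, HiSCR75, flare and worst skin pain response, and refers to Section 9.3.2 for its definition. Section 9.3.2 introduces a grouping for efficacy subgroups with the words "the following categories can also be used". It has three classes:

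- **ADAb positive** needs positive results at two or more on-treatment time points, with Baseline and SFU not counted.
- **ADAb negative** has three routes. The first is all samples negative and none missing or inconclusive. The second is "Only 1 sample is ADAb positive and all other samples (including Baseline) are ADAb negative or missing or inconclusive". The third is "Only 1 sample is missing or inconclusive and the remaining ADAb samples are negative".
- **ADAb missing** is the remainder: "Defined as study participants who do not fulfil the criteria for one of the 2 groups listed above".

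The reason given for requiring two time points is "to exclude those study participants who have only one occurrence of ADAb levels during the course of treatment". The same section has a separate overall ADAb status: "Positive if the study participant has at least one positive sample up to the time point of interest". It also defines an inconclusive sample as one without a confirmed positive result where the drug concentration exceeds the assay's tolerance limit.

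**The concern.** The second and third routes to ADAb negative treat missing information differently. With no positive sample, two unreadable samples are enough to withhold the negative label. With one confirmed positive, any number of unreadable samples still gives it. The participant with more evidence of antibody gets the more negative label. An inconclusive sample means that the drug level prevented a negative conclusion, so it cannot support one.

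The subgroup exists to show whether antibodies reduce response. Under Sections 3.9 and 4.2.1.1, stopping treatment for an AE or lack of efficacy is set to nonresponse. When such a participant has one positive sample and little else, the rule takes a nonresponder out of the positive side and adds one to the negative side. Both moves shrink an ADAb-related deficit.

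**Working it through.** The SAP states no figure for this rule, so there is none to reproduce. The check has two parts.

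**1. The rules applied to sample patterns** (Baseline negative; scheduled post-Baseline samples at Weeks 4, 8, 12, 16, 20, 24, 36 and 48)

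| Pattern | Efficacy grouping | Overall status |
|---|---|---|
| Positive at Week 4, seven others missing or inconclusive | Negative | Positive |
| Negative at Week 4, seven others missing | Missing | Missing |
| No positive, two missing, six negative | Missing | Missing |
| One positive, seven negative | Negative | Positive |
| Positive at Week 4 and at PEOT (mapped to Week 8), six missing | Positive | Positive |

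The first row against the second and third is the defect. The fourth row is the transient positive that the two-time-point rule is meant for. The last row assumes that the PEOT sample counts as on treatment.

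**2. Size, on assumed inputs**

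Take 100 bimekizumab participants: 40 ever-positive with 20 responders (50%) and 60 never-positive with 36 responders (60%). The full contrast is -10 points. Let k of the 40 leave early as nonresponders after one positive sample, and m of the 60 leave early as nonresponders with two or more missing samples. As written, the k go to ADAb negative and the m go to ADAb missing:

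- positive group: 20/(40 - k)
- negative group: 36/(60 - m + k)

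With equal early-leaver shares (m/60 = k/40):

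| Share | k, m | Positive | Negative | Difference |
|---|---|---|---|---|
| 5% | 2, 3 | 20/38 = 52.6% | 36/59 = 61.0% | -8.4 |
| 10% | 4, 6 | 20/36 = 55.6% | 36/58 = 62.1% | -6.5 |
| 20% | 8, 12 | 20/32 = 62.5% | 36/56 = 64.3% | -1.8 |

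If no never-positive participant leaves early, or if such leavers stay in ADAb negative, the negative rate is 36/(60 + k). The differences are then 52.6 - 58.1 = -5.4, 55.6 - 56.3 = -0.7 and 62.5 - 52.9 = +9.6.

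A second example uses the pooled arms of Table 2-1 (N=280, HiSCR50 0.60). Assume 40% ever-positive (112), 10% of them leaving early (11.2), and 60% response among all others. The any-positive contrast is 0.9 × 60 = 54.0% v 60.0%, or -6.0 points.

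- Early leavers among positives only: 60.0% v 100.8/(168 + 11.2) = 56.25%, or +3.75.
- 10% of never-positives also leaving early, with their 60% overall rate kept: 60.0% v 100.8/(168 - 16.8 + 11.2) = 62.1%, or -2.1.

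**3. Effect of moving the k out of ADAb negative**

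In the second example with leavers among positives only, the result is 60.0% v 60.0%. The negative group is clean, but the 6-point deficit is still hidden. A repeat by overall status, with no never-positive leavers, restores 54.0% v 60.0%. That repeat has its own lean, because overall status also sends never-positive leavers with more than one missing sample to missing. In the first example at 10% it gives 20/40 = 50.0% v 36/54 = 66.7%, or -16.7 points. The two tables should be read together.

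**The case against.** Much of the case on the other side stands, and it limits the size.

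- **Sign reversal.** A reader might infer that the rule reverses the ADAb effect. That needs early leavers mainly among positives, or never-positive leavers kept in ADAb negative. As written, never-positive leavers with two or more missing samples go to ADAb missing, which raises the negative group's rate and works the other way.
- **Week 4 positives who stop.** A reader might infer that they are always called negative. A PEOT sample is planned, and Section 3.2.2 assigns it to the next ADAb visit, so a second positive there can make the participant positive. The defect affects those whose only positive is their last sample, whose PEOT sample is missing or inconclusive, or whose other samples are inconclusive.
- **Contradiction with the rationale.** The next sentence of Section 9.3.2 shows that exclusion means exclusion from the positive group, and the rule does that. The rationale does not, however, extend to one positive among unobserved samples.
- **Contradiction with overall status.** These are two named classifications with different purposes, so their disagreement is not an error.
- **Weight.** Only antibiotic rescue and stopping for an AE or lack of efficacy are set to nonresponse; missing data after other dropouts are multiply imputed. Section 4.8 makes the summaries descriptive, and the grouping is introduced as an additional option.

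None of this explains why one positive plus many unreadable samples should be negative when no positive plus two is missing.

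**Conclusion.** The point holds as a flaw in a classification rule, with attenuation as its consequence. On the assumed inputs and equal early-leaver shares of 5% to 20%, a 10-point deficit shows as 8.4 down to 1.8 points. ADAb prevalence, early-leaver share and response by ADAb status are all assumptions, since the SAP gives none of them. The figures also assume that scheduled samples after stopping count as missing and that every such leaver is a nonresponder. They ignore second positives from PEOT samples and multiple imputation, both of which reduce the effect. No primary or secondary conclusion depends on this subgroup. It should still be corrected, because the table is meant to inform on loss of efficacy with antibodies and its error leans towards reassurance.

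**What to change.** In Section 9.3.2, allow the second route to ADAb negative only when at most one other sample is missing or inconclusive, as the third route already does. Put participants with one on-treatment positive and more missing or inconclusive samples in ADAb missing, or in a separate single-positive (indeterminate) group. A positive at Baseline only should not count as an on-treatment positive.

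This cleans the negative group but does not by itself undo the masking. So repeat the Week 16 ADAb subgroup tables with the overall ADAb status, using samples up to Week 16. State in Section 4.8 which grouping is the main one.

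The cost is a short wording change, one derivation and one extra set of tables. The downside is that a few transient positives count as positive in the repeat.
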